### 5.3.3 Pharmacokinetic Assessments

Blood samples for the PK evaluation of both cabiralizumab and nivolumab will be collected from all patients.

Patients enrolled in Phase 1a and Phase 1b will have blood drawn for measurement of serum cabiralizumab concentration. Blood samples will be collected during Cycle 1 and Cycle 8 on Days 1, 2, 4, and 8 as well as both before and after infusion for Cycle 2, 3 and 4. In addition, blood samples will be collected before the infusion on Cycles 5, 9, 13, and 21, then every 6 cycles while on treatment. A blood sample will also be collected for PK analysis during the End-of-Treatment Follow-up Period (28 [±7] days and 100 [±7] days post-last dose).

Patients enrolled in the 3-week dosing regimen cohort (1aD) will have additional blood sample drawn on Day 15 of Cycles 1 and 8. See Appendix C for specific collection time points.

Patients enrolled in Phase 1a and Phase 1b combination cohorts will have blood drawn for measurement of serum nivolumab concentration. Blood samples will be collected both before and at the end of infusion for Cycle 1 to Cycle 4. In addition, blood samples will be collected at the end of the infusion for Cycle 8 and before the infusion on Cycles 5, 9, 13, and 21. A blood sample will also be collected during the End-of-Treatment Follow-up Period.

Standard PK parameters will be determined based on serum cabiralizumab concentration-time data, as appropriate. Nivolumab accumulation will be evaluated as appropriate.

#### 5.3.3.1 Pharmacokinetic Collection and processing

Blood samples will be collected and processed for serum according to the instructions provided in a Laboratory Manual.

#### 5.3.3.2 Pharmacokinetic Sample Analysis

Cabiralizumab concentration in serum will be determined in serum using a validated ELISA method. Nivolumab concentration in serum will be determined in serum using a validated ECLA method.

### 5.3.4 Immunogenicity Assessments

Blood samples will be collected before the infusion on Cycles 1, 2, 3, 4, 5, 9, 13, and 21, and at the 28 (±7) days and 100 (±7) days End-of-Treatment Visits to measure ADA for cabiralizumab and nivolumab. ADA for cabiralizumab in serum will be measured by a validated bridging ECLA that utilizes Meso Scale Discovery (MSD) technology. ADA for nivolumab in serum will be measured by a validated ECLA method.

### 5.3.5 Biomarker Assessments

A variety of factors that could potentially predict clinical response to the combination of cabiralizumab and nivolumab will be investigated in peripheral blood and in tumor specimens

collected from patients prior to and during treatment. Data from these investigations will be evaluated for associations with response and/or safety (AE) data. In addition, analyses of markers between the treatment arms will provide the necessary data to identify and validate biomarkers with predictive vs prognostic value. Complete instructions on the collection, processing, handling and shipment of all samples described herein will be provided in a Laboratory Manual.

#### 5.3.5.1 Skin Tissue and Tumor Tissue Specimens

Tumor tissue specimens in the form of a paraffin embedded block or unstained slides will be submitted for central IHC assessment. These biopsy samples should be excisional, incisional or core needle as fine needle aspirates or other cytology specimens are insufficient for downstream biomarker analyses. Tissue samples are being collected to evaluate the PD effect of study drugs on the tumor microenvironment.

Skin and tumor biopsy specimens will be obtained before treatment and on-treatment to examine immune infiltrates and expression of selected tumor markers. Optional skin and tumor biopsies may be obtained upon documentation of tumors that have responded and/or progressed on or after treatment to understand mechanisms of resistance.

Samples may be assessed for the expression of immune or disease related genes and/or proteins, as well as for the presence of immune cell populations using a variety of methodologies including but not limited to IHC, qRT-PCR, genetic mutation detection, and *in situ* hybridization (ISH). Other methods of tumor biomarker expression are being evaluated.

#### 5.3.5.2 Serum

In addition to the PK and ADA analyses mentioned above, serum samples will be analyzed to determine the PD effect of study drugs on cytokine and CSF1R ligand concentrations. Samples may be assessed by ELISA, seromics, and/or other relevant multiplex-based protein assay methods. Serum marker analyses may also help establish a biomarker signature that may predict benefit or correlate with efficacy that can be used to inform this and future studies. Timings of sample collection are listed in [Appendix C](#) and analyses to be performed are described in [Appendix D](#).

#### 5.3.5.4 Flow Cytometry

Pre-treatment and on-treatment whole blood and PBMC samples will be analyzed by flow cytometry to study the effects of cabiralizumab and nivolumab on various peripheral blood immune cell subsets. Whole blood samples will be assessed to confirm the predicted PD effect of cabiralizumab on the reduction of CD16+ monocytes. PBMC samples will be analyzed to determine whether blockade of PD-1 combined with CSF1R targeting will impact peripheral T-cell levels and activation status.

Timing of sample collection is listed in [Appendix C](#) and analyses to be performed are described in [Appendix D](#).

## 6. Adverse Events

An *Adverse Event (AE)* is defined as any new untoward medical occurrence or worsening of a preexisting medical condition in a clinical investigation, patient-administered study drug and that does not necessarily have a causal relationship with this treatment. An AE can therefore be any unfavorable and unintended sign (such as an abnormal laboratory finding), symptom, or disease temporally associated with the use of study drug, whether or not considered related to the study drug.

The causal relationship to study drug is determined by an investigator and should be used to assess all AEs. The causal relationship can be one of the following:

- Related: There is a reasonable causal relationship between study drug administration and the AE.
- Not related: There is not a reasonable causal relationship between study drug administration and the AE.

The term “reasonable causal relationship” means there is evidence to suggest a causal relationship.

AEs can be spontaneously reported or elicited during open-ended questioning, examination, or evaluation of a patient. (In order to prevent reporting bias, patients should not be questioned regarding the specific occurrence of one or more AEs.)

### 6.1 Collection of Adverse Events

Any new symptoms, injury or worsening of symptoms that occur following signing of the informed consent form (ICF) but prior to first infusion (Cycle 1 Day 1) will be considered pretreatment events and reported on the Medical History page of the electronic case report form (eCRF), unless they directly correlate to a study-related procedure. Adverse event reporting will continue until 100 ( $\pm 7$ ) days after the last dose of study drug or until initiation of subsequent anti-cancer therapy.

### 6.2 Serious Adverse Events

A *Serious Adverse Event (SAE)* is any untoward medical occurrence that at any dose:

- Results in death. Death may occur as a result of the underlying disease process. All events other than progression of underlying disease that result in death during the reporting period up to 100 ( $\pm 7$ ) days after the last dose of cabiralizumab (or until initiation of subsequent anti-cancer therapy) must be treated as an SAE and reported as such.
- Is life-threatening (defined as an event in which the patient was at risk of death at the time of the event)
- Requires inpatient hospitalization or causes prolongation of existing hospitalization (see NOTE below)

- Results in persistent or significant disability/incapacity
- Is a congenital anomaly/birth defect
- Is an important medical event (defined as a medical event that may not be immediately life-threatening or result in death or hospitalization but, based upon appropriate medical and scientific judgment, may jeopardize the patient or may require intervention [e.g., medical, surgical] to prevent one of the other serious outcomes listed in the definition above.) Examples of such events include, but are not limited to, intensive treatment in an emergency room or at home for allergic bronchospasm; blood dyscrasias or convulsions that do not result in hospitalization.) Potential drug-induced liver injury (DILI) is also considered an important medical event. (See Section 6.7 for the definition of potential DILIs.)

Suspected transmission of an infectious agent (e.g., pathogenic or nonpathogenic) via the study drug is an SAE.

Although pregnancy and potential DILI are not always serious by regulatory definition, these events must be handled as SAEs. (See Section 6.2.1 for reporting pregnancies).

**Note:** The following hospitalizations are not considered SAEs in this clinical study:

- Visit to the emergency room or other hospital department <24 hours, that does not result in admission (unless considered an important medical or life-threatening event)
- Elective surgery, planned prior to signing consent
- Admissions as per protocol for a planned medical/surgical procedure
- Routine health assessment requiring admission for baseline/trending of health status (e.g., routine colonoscopy)
- Medical/surgical admission other than to remedy ill health and planned prior to entry into the study. Appropriate documentation is required in these cases.
- Admission encountered for another life circumstance that carries no bearing on health status and requires no medical/surgical intervention (e.g., lack of housing, economic inadequacy, caregiver respite, family circumstances, administrative reason).
- Admission for administration of anti-cancer therapy in the absence of any other SAEs
- Hospitalization for an event solely related to disease progression or for an elective or planned procedure to treat a pre-existing condition
- Admission to hospice or care facility to support activities of daily living

### 6.2.1 Serious Adverse Event Reporting

The Investigator should report any SAE that occurs after the first study drug dose and until 100 ( $\pm 7$ ) days after the last dose of study drug or until initiation of subsequent anti-cancer therapy. Protocol-specified procedure related SAE will be collected following signing of ICF.

An SAE report should be completed for any event where doubt exists regarding its seriousness.

If the Investigator believes that an SAE is not related to study drug, but is potentially related to the conditions of the study (such as withdrawal of previous therapy or a complication of a study procedure), the relationship should be specified in the narrative section of the SAE Report Form.

- SAEs, related or unrelated to study drug, and pregnancies must be reported to the Sponsor (or designee) within 24 hours of becoming aware of the event. SAEs must be recorded on the SAE Report Form, and pregnancies must be recorded on a Pregnancy Surveillance Form (paper forms). SAE and pregnancy data reporting must be done on the paper SAE/Pregnancy Surveillance Forms provided by the Sponsor (or designee). They are to be transmitted via email or fax [REDACTED]

[REDACTED]  
[REDACTED]  
[REDACTED]

If only limited information is initially available, follow-up reports are required.

**Note:** Follow-up SAE reports should include the same Investigator term(s) initially reported.

If an ongoing SAE changes in intensity or relationship to study drug or if new information becomes available, a follow-up SAE report should be sent within 24 hours to the Sponsor (or designee) using the same procedure used for transmitting the initial SAE report.

All SAEs should be followed to resolution or stabilization.

### 6.3 Non-Serious Adverse Events

A *non-serious adverse event* is any AE not classified as serious.

#### 6.3.1 Non-serious Adverse Event Reporting

Non-serious AEs should also be followed to resolution or stabilization, or reported as SAEs if they become serious (see Section 6.2.1). Follow-up is also required for non-serious AEs that cause interruption or discontinuation of study drug and for those present at the end-of-study treatment, as appropriate. All identified non-serious AEs must be recorded and described on the appropriate AE page of the CRF.

Completion of supplemental CRFs may be requested for AEs and/or laboratory abnormalities that are reported during the course of the study.

#### **6.4 Laboratory Test Result Abnormalities**

The following laboratory test result abnormalities should be captured on the appropriate CRF page or SAE Report Form as appropriate:

- Any laboratory test result that is clinically significant or meets the definition of an SAE
- Any laboratory test result abnormality that required the patient to have study drug discontinued or interrupted
- Any laboratory test result abnormality that required the patient to receive specific corrective therapy.

It is expected that wherever possible, the clinical rather than laboratory term would be used by the reporting Investigator (e.g., anemia versus low hemoglobin value).

#### **6.5 Pregnancy**

If, following initiation of the investigational product, it is discovered that a study patient is pregnant or may have been pregnant at the time of investigational product exposure, including during at least 5 half-lives (90 days) after product administration, the investigational product will be permanently discontinued in an appropriate manner.

The Investigator must immediately notify the Sponsor's (or designee's) Medical Monitor of this event and complete and forward a Pregnancy Form to the Sponsor (or designee) within 24 hours and in accordance with SAE reporting procedures described in Section 6.2.1.

Follow-up information regarding the course of the pregnancy, including perinatal and neonatal outcome and, where applicable, offspring information, must be reported on the Pregnancy Surveillance Form.

Any pregnancy that occurs in a female partner of a male study participant should be reported to the Sponsor. Information on this pregnancy will be collected on the Pregnancy Surveillance Form.

#### **6.6 Overdose**

Any dose of study drug in excess of 50% of the dose level specified in the protocol is considered to be an overdose. Signs and symptoms of an overdose that meet any SAE criterion must be reported as an SAE in the appropriate time frame and documented as clinical sequelae to an overdose. There is no known antidote for a drug overdose to either cabiralizumab or nivolumab. In the event of an overdose, patients should be closely monitored and given appropriate supportive treatment.

## 6.7 Potential Drug Induced Liver Injury

Wherever possible, timely confirmation of initial liver-related laboratory abnormalities should occur prior to the reporting of a potential drug-induced liver injury (DILI) event. All occurrences of potential DILIs, meeting the defined criteria, must be reported as SAEs.

Potential drug induced liver injury is defined as:

1. ALT or AST elevation >3x ULN  
*and*
2. Total bilirubin >2x ULN without initial findings of cholestasis (elevated serum alkaline phosphatase) *or* INR > 1.5 xULN (in the absence of anticoagulation)  
*and*
3. No other immediately apparent possible causes of aminotransferase elevation and hyperbilirubinemia including but not limited to viral hepatitis, pre-existing chronic or acute liver disease, or the administration of other drugs known to be hepatotoxic.

## 7. Statistical Considerations

All analyses will be descriptive and will be presented by dose group and overall as appropriate. Data collected in this study will be presented using summary tables and patient data listings. Continuous variables will be summarized using descriptive statistics, specifically the mean, median, standard deviation, minimum, and maximum. Categorical variables will be summarized by frequencies and percentages.

### 7.1 Sample Size Determination

Approximately 85 patients will be enrolled in Phase 1a. In dose escalation, between 3 and 9 patients are expected to be treated at each dose escalation cohort according to the algorithm outlined in Table 2 . There will also be up to 40 patients enrolled into the exploratory dose cohorts to further explore safety, PK, and PD, and approximately 10 patients enrolled into the 3-week dosing regimen cohort to characterize the PK and safety profile at a 3-week dosing schedule. In Phase 1b, approximately 210 patients will be enrolled.

### 7.2 Populations for Analyses

- **Enrolled Population:** All patients who sign the ICF and are approved for enrollment by sponsor or designee, and for Phase 1b patients only, are registered in IXRS.
- **Evaluable Population:** Patients who have a measureable lesion at baseline and have at least 1 post-baseline tumor assessment or patients with the clinical progression or experiencing death event without any post baseline tumor assessment.
- **Safety Population:** All patients who receive at least one dose of cabiralizumab and/or nivolumab.
- **PK Population:** All patients who receive at least one dose of cabiralizumab and/or nivolumab and have available serum concentration data.
- **Biomarker Patients:** All patients who receive at least one dose of cabiralizumab and/or nivolumab and have available biomarker data.
- **Immunogenicity Patients:** All patients who receive at least one dose of cabiralizumab and/or nivolumab and have available ADA data.

### 7.3 Endpoints

#### 7.3.1 Phase 1a Endpoints

##### 7.3.1.1 Primary

- **Safety**
  - The incidence of Grade 3 and Grade 4 AEs and clinical laboratory abnormalities defined as DLTs
  - The incidence of AEs, clinical laboratory abnormalities, and ECG abnormalities

### 7.3.1.2 Secondary

- **Pharmacokinetic:** The following PK parameters will be derived from concentration-time data for cabiralizumab when appropriate and applicable. Other parameters, such as dose dependency and accumulation ratio, may also be calculated. Accumulation ratio of Cmax and Cmin for nivolumab may be calculated if the data are available.
  - Area under serum concentration-time curve (AUC)
  - Maximum serum concentration (Cmax)
  - Minimum serum concentration (Cmin)
  - Clearance (CL)
  - Volume of distribution at steady state (Vss)
- **Immunogenicity:** Defined as an immune response to either cabiralizumab or nivolumab, will be assessed by measurement of total anti-FPA008 antibodies and total anti-nivolumab antibodies from all patients. Immunogenicity testing will consist of screening, confirmation, and titration for both cabiralizumab and nivolumab.
- **Pharmacodynamic Biomarkers**
  - Changes in whole blood monocyte subsets by flow cytometry
  - Changes in cytokine levels by multiplex analysis
  - Change in macrophage and T-cell levels in tumor biopsy samples

### 7.3.2 Phase 1b Endpoints

#### 7.3.2.1 Primary

- **Efficacy**
  - ORR will be defined as the total number of patients with confirmed responses of either CR or PR divided by the total number of patients who are evaluable for a response per RECIST v1.1 by investigator assessment

- Safety
  - The incidence of AEs, SAEs, clinical laboratory abnormalities, and ECG abnormalities
  - The incidence of treatment discontinuations, modifications, and interruptions due to adverse events
  - Grade 3 and Grade 4 AEs and clinical laboratory abnormalities

### 7.3.2.2 Secondary

- **Pharmacokinetic:** The following PK parameters will be derived from concentration-time data for cabiralizumab when appropriate and applicable. Other parameters, such as dose dependency and accumulation ratio, may also be calculated. Accumulation ratio of  $C_{max}$  and  $C_{min}$  for nivolumab may be calculated if the data are available.
  - Area under serum concentration-time curve (AUC)
  - Maximum serum concentration ( $C_{max}$ )
  - Minimum serum concentration ( $C_{min}$ )
  - Clearance (CL)
  - Volume of distribution at steady state ( $V_{ss}$ )
- **Immunogenicity:** Defined as an immune response to either cabiralizumab or nivolumab, will be assessed by measurement of total anti-FPA008 antibodies and total anti-nivolumab antibodies from all patients. Immunogenicity testing will consist of screening, confirmation, and titration for both cabiralizumab and nivolumab. The results will be classified into incidence of ADA at baseline and after initiation of treatment.
- Pharmacodynamic Biomarkers
  - Changes in whole blood monocyte subsets by flow cytometry
  - Changes in cytokine levels by multiplex analysis
  - Change in macrophage and T-cell levels in tumor biopsy samples
- Efficacy
  - OS will be defined as the time between the first dose of study drug and death.
    - One-year OS rate
    - Median OS
  - DOR will be defined as the time from response (CR or PR) until the first objectively documented PD per RECIST v1.1
  - PFS will be defined for each patient as the time from the first dose to the first objectively documented of disease progression per RECIST v1.1 or death due to any cause.

- ORR by Central Imaging Review

[REDACTED]

- [REDACTED]
- [REDACTED]
- [REDACTED]
- [REDACTED]
- [REDACTED]

## 7.4 Analyses

### 7.4.1 Demographics and Baseline Characteristics

Demographic data, medical history, other baseline characteristics, concomitant disease, and concomitant medication will be summarized by cohort and overall. To determine whether the criteria for study conduct are met, corresponding tables and listings will be provided. These will include an assessment of protocol deviations, study drug accountability, and other data that may impact the general conduct of the study.

### 7.4.2 Efficacy Analyses

For each disease type, response to treatment will be summarized for ORR, defined as the ratio of the number of patients that achieve an objective response (a BOR of CR or PR) to total number of patients who are evaluable for a response. Exact confidence interval will be constructed for the response rate. Overall Survival, survival at 1 year, and median survival will be estimated by the Kaplan-Meier method. The corresponding confidence interval will also be presented.

### 7.4.3 Safety Analyses

Safety analyses will be performed for patients included in the safety population. Incidence of AEs, clinical laboratory information, vital signs, ECOG performance status, weight, and ECGs will be tabulated and summarized.

Incidence of AEs will be summarized overall and with separate summaries for SAEs, AEs leading to discontinuation, AEs leading to death, and NCI-CTCAE v 4.03 Grade 3 or higher AEs.

Weight and vital signs will be summarized descriptively (n, mean, standard deviation, median, minimum, and maximum). ECOG performance status will be summarized categorically and descriptively.

Shift tables displaying patient counts and percentages classified by baseline grade and maximum grade on treatment will be provided for laboratory data by cohort and overall. A marked laboratory change is defined as a shift from a baseline Grade 0 to Grade 3 (non-hematologic) or

Grade 4 (hematologic) on treatment, or a shift from a baseline Grade 1 to Grade 4 on treatment. The number and percentage of patients with marked laboratory changes will be tabulated by cohort and overall.

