### Summary:

The number (%) of subjects with the following will be summarized using the worst CTC grade ontreatment per subject.

- Post-baseline grade (summary of worst toxicity grade)
- Grade change from baseline
- Descriptive statistics of laboratory test result and their changes from baseline at scheduled nominal visit.

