## 7.6.7.3 Abnormal Laboratory Test

## Summary:

The number of subjects with the following laboratory abnormalities from on-treatment evaluations will be summarized:

• CK > 10 x ULN, > 15 x ULN, > 20 x ULN

• LDH > 10 x ULN, > 15 x ULN, > 20 x ULN

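### As worded, the marked laboratory change rule counts a non-hematologic shift from Grade 0 to 3 but not the larger shift from Grade 0 to 4

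*Protocol*

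**What the plan says.** Protocol Section 7.4.3 plans two laboratory outputs in one paragraph.

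- The first is a full cross-classification, for each cohort and for all patients together: "Shift tables displaying patient counts and percentages classified by baseline grade and maximum grade on treatment will be provided for laboratory data".
- The second is a summary category. Its definition begins "A marked laboratory change is defined as a shift from a baseline Grade 0 to Grade 3 (non-hematologic) or" and continues "Grade 4 (hematologic) on treatment, or a shift from a baseline Grade 1 to Grade 4 on treatment". The commitment attached to it is "The number and percentage of patients with marked laboratory changes will be tabulated by cohort and overall".

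So three shifts qualify: Grade 0 to 3 for non-hematologic tests, Grade 0 to 4 for hematologic tests, and Grade 1 to 4 with no restriction on test type.

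SAP Section 7.6.7 does not use the term. Its laboratory summary lists "Post-baseline grade (summary of worst toxicity grade") and "Grade change from baseline", both based on the worst on-treatment grade per subject. SAP Sections 7.6.7.1 and 7.6.7.3 add threshold counts for hepatic tests, CK and LDH.

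**The concern.** A category meant to pick out large deteriorations should not drop a patient for deteriorating further. Here the non-hematologic clause names one end grade, Grade 3, with nothing to say that Grade 4 also qualifies. The Grade 4 clause that follows is labelled hematologic, and the last clause needs a Grade 1 baseline. The only four-grade worsening on a non-hematologic test is left without a clause.

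The cell may well be occupied in this trial. Protocol Section 3.1.2.1 reports dose-limiting toxicities from laboratory abnormalities, after which the laboratory cutoffs were raised. Section 4.3.5 foresees Grade 4 CK values. Exclusion criterion 1 in Section 3.2.3 keeps out patients with conditions known to raise CK, so a normal CK at baseline should be common. None of these passages gives a grade frequency.

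At stake is a promised count and percentage, by cohort and overall, that would be wrong if programmed as written.

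**Working it through.** The plan states no figure for this category, so there is nothing to reproduce. The check runs the rule over every possible worsening.

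**Inputs.** The rule and the maximum-grade basis come from Protocol Section 7.4.3. Planned sizes come from Protocol Section 3.2.1: about 30 per Phase 1b cohort, 210 in Phase 1b and 295 overall.

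**Step 1: cells.** With grades 0 to 4, the worsening cells number 4 + 3 + 2 + 1 = 10 for each type of test. Shift size is maximum grade minus baseline grade.

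| Baseline to maximum | Shift (grades) | Non-hematologic, as written | Non-hematologic, with *or higher* | Hematologic |
|---|---|---|---|---|
| 0 to 1 | 1 | no | no | no |
| 0 to 2 | 2 | no | no | no |
| 0 to 3 | 3 | **yes** | **yes** | no |
| 0 to 4 | 4 | **no** | **yes** | **yes** |
| 1 to 2 | 1 | no | no | no |
| 1 to 3 | 2 | no | no | no |
| 1 to 4 | 3 | **yes** | **yes** | **yes** |
| 2 to 3 | 1 | no | no | no |
| 2 to 4 | 2 | no | no | no |
| 3 to 4 | 1 | no | no | no |
| **Flagged** | | 2 of 10 | 3 of 10 | 2 of 10 |

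**Step 2: ordering.** For non-hematologic tests the flagged shifts are 3 − 0 = 3 and 4 − 1 = 3 grades. The unflagged 0 to 4 shift is 4 − 0 = 4 grades. Adding *or higher* flags exactly the shifts of 3 grades or more. The hematologic column needs no change: both flagged shifts end at Grade 4, and the largest is included.

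**Step 3: direction of the error.** Take a patient with baseline Grade 0 and a maximum of Grade 3, who is counted. If a later value reaches Grade 4, the maximum becomes 4 and the patient leaves the numerator. With n patients, the percentage falls by 1/n:

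- one cohort: 1/30 = 3.3 percentage points
- all Phase 1b: 1/210 = 0.5 points
- whole study: 1/295 = 0.3 points

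**Step 4: illustration with assumed counts.** Suppose 4 of 30 patients shift 0 to 3 and k shift 0 to 4 on one non-hematologic test, with no other qualifying shift. As written the table shows 4/30 = 13.3% whatever k is. The corrected figure is (4 + k)/30:

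| k (assumed) | As written | Corrected | Difference (points) |
|---|---|---|---|
| 0 | 13.3% | 4/30 = 13.3% | 0 |
| 1 | 13.3% | 5/30 = 16.7% | 3.3 |
| 2 | 13.3% | 6/30 = 20.0% | 6.7 |
| 4 | 13.3% | 8/30 = 26.7% | 13.3 |

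The documents contain no laboratory grade frequencies, so no value of k is better supported than another.

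**The case against.** The best defence is that a sensible programmer would read Grade 3 as at least Grade 3. That may happen, but the text does not support it. The same section says Grade 3 or higher when describing the adverse event summary, and the dose-limiting toxicity definition in Section 3.1.2.1.1 uses an at-or-above sign. Where the authors mean a threshold, they write one.

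A second defence is that the definition does not itself repeat the word maximum. If any on-treatment value could qualify, a patient with both a Grade 3 and a Grade 4 result would be counted. That narrows the gap without closing it, since a patient with no recorded Grade 3 value is still missed. It also departs from the basis set in the sentence just before.

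A third defence is that nothing severe is hidden, and this one stands. The shift tables show the 0 to 4 cell. The Phase 1b primary safety endpoints list "Grade 3 and Grade 4 AEs and clinical laboratory abnormalities" separately from this category. The SAP reports worst grade whatever the baseline, and gives counts such as "CK > 10 x ULN, > 15 x ULN, > 20 x ULN". A reader might infer that severe laboratory abnormalities are undercounted in the trial's reporting. The documents do not support that: the category measures change from baseline, and only its own percentage is affected.

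A reader might also infer that leaving out Grade 2 to 4 or Grade 1 to 3 is the same mistake. It is not. Both are two-grade shifts, and every shift the rule counts is at least three grades. Adding one of them would be a preference.

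**Conclusion.** The point holds in a narrow form. Taken as written and on the maximum-grade basis, the definition misses the non-hematologic shift from Grade 0 to 4 while counting two smaller shifts. The resulting number and percentage can move the wrong way as a patient gets worse.

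It is a minor matter. It touches one descriptive table and no efficacy result, dose-limiting toxicity assessment or dose decision. The size of the undercount cannot be computed from the documents.

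The conclusion rests on two assumptions: that Grade 3 is programmed as exactly Grade 3, and that the protocol's table is produced. The second is uncertain, because the SAP neither specifies the table nor says that it has been dropped. It would therefore go too far to say that the SAP's planned output is wrong. The SAP simply leaves the protocol's commitment unaddressed.

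**What to change.** In Protocol Section 7.4.3, change the first clause to *Grade 0 to Grade 3 or higher* for non-hematologic tests, and state in the definition that the maximum on-treatment grade is used. Leave the hematologic and Grade 1 to 4 clauses as they are.

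In SAP Section 7.6.7, either carry the corrected definition with one table row by cohort and overall, or state that the marked-change table is dropped in favour of the worst-grade and grade-change summaries.

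The cost is a few words in the protocol and one row definition or one sentence in the SAP. No added data, patients or procedures are needed.
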